## 5.2 Secondary Study Outcomes

Secondary outcomes will include three of the individual components of the Modified Vesikari Score considered independently and one additional measure of burden of illness. Specifically, they are:

1. **Diarrhea duration:** Time from randomization until the appearance of the last watery stool as reported during daily surveys.
2. **Vomiting duration:** Time from randomization until the last vomiting episode as reported during daily surveys. Vomiting duration is only evaluated in children who vomited  $\geq 3$  times during the 24 hours prior to the emergency department visit.

3. **Return visits:** Return visits for unscheduled care to a healthcare provider related to vomiting, diarrhea, dehydration, fever, or fluid refusal, within 2 weeks of the index visit. Scheduled visits (e.g. reassessment, vaccinations, unrelated issues) will not be included.
4. **Missed daycare:** Days of daycare missed by subjects who attend daycare.
5. **Missed work:** Days of work missed by caregivers who work outside of the home.
6. **Household transmission rate:** A household census will be obtained at the time of enrollment, and information about household contacts symptoms will be obtained during daily surveys to determine household transmission rate.

The overall significance level for statistical tests on the secondary outcomes will be set at 0.05. Holm's method will be used to adjust for multiple comparisons. The continuous variables of duration of diarrhea and duration of vomiting (measured in hours and analyzed with a Van Elteren test), will be stratified by clinical center. Similarly, the number of days the child is absent from daycare and the caregiver is absent from work will be analyzed with a Van Elteren test, stratified by clinical center and etiology.

Dichotomous outcomes to be evaluated include emergency department acute gastroenteritis-related revisits, intravenous rehydration, and hospitalization. Additional analyses involving these outcomes will include linear and logistic regression models that adjust for possible effects of baseline characteristics.

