### 3.4 Follow Up Data Collection

Successful follow up will be maximized by obtaining multiple phone numbers for families and emergency contacts, scheduling calls and sending phone text reminders, allowing for electronic completion and centralizing all follow-up procedures at the lead institution (Washington University). Trained, experienced study staff will contact the family daily (including weekends) until both the diarrhea and vomiting have resolved and the treatment has been completed on day 5. Additional contact will be made on day 14 for outcome assessment, and months 1, 3, 6, 9 and 12 for long term safety outcomes. Study staff will use a standardized data collection form, and will inquire about ongoing symptoms, medical evaluations, treatments, child care, work absenteeism, and side effects. Detailed questioning will follow positive responses. A study diary will be provided to caregivers to use as a note-taking tool. Caregivers may also be provided an option of completing the follow-up collection electronically. Patient compliance with study drug administration will be assessed on day 5. To maximize compliance, caregivers will be reminded of the importance and method of administering the study drug. On day 14, the study site staff (not the central staff conducting the follow up) will perform a chart review for final data collection and identification of recorded adverse events during the 14 day study period. Adverse event reporting is described in detail in Section 8.3 on page 33.

Every effort will be made complete daily follow-up on the day necessary. However, if one or two days of follow-up contact is missed, data for those missed days may be collected on the next contact, if the caregiver used the home diaries or can recall the information. If all contact is missed but then the parent is contacted on day 14, follow-up data for the daily calls will be collected only if the parent diaries were used. For day 5 and 14, contact may be made within + 3 days. For month 1, 3, 6, 9, and 12 follow-up, contact may be made within  $\pm 2$  weeks.

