## Initial Study Drug Administration

Clinical staff in the emergency department will administer the first dose of study drug by sprinkling the capsule's contents into 20-30 mL of room temperature non-carbonated liquid. Capsule contents may also be sprinkled into 1 tablespoon of applesauce as an alternative to liquid. Oral fluid therapy will be encouraged according to sites' existing clinical guidelines. At discharge, parents will also be provided with clinical instructions concerning what and how much fluid to drink, criteria for returning to the emergency department or seeing their physician, and other standardized discharge instructions for acute gastroenteritis. Study research coordinators will provide the parents with instructions concerning study drug administration at home, completion of study forms, and a letter for their pediatrician that explains the study. The importance of administering all doses dispensed and the need to communicate with the study team on a daily basis until symptoms resolve will be stressed.

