## 7.4 Protections Against Potential Risks

Several steps will be taken to minimize the risks of participation in the study. All of the participating clinical centers are tertiary pediatric hospitals with highly trained pediatric staff. Subjects will be closely followed after discharge. Families will be contacted daily until both the diarrhea and vomiting have resolved and the treatment has been completed. Additional contact will be made on day 14, and months 1, 3, 6, 9 and 12 for long term safety outcomes. Parents or legally authorized representatives will also receive specific instructions as to when to see a health care provider. If an adverse event is reported at the time of follow-up, research personnel will refer subjects for appropriate medical care, when applicable.

Loss of confidentiality will be mitigated by the use of the PECARN Data Coordinating Center which has a highly secure IT infrastructure, and by the existence of trained research staff at participating sites. Data security is described in Section 6.

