## 5.4 Multiple Comparisons

The secondary outcomes will be subject to adjustment of significance level for multiple comparisons. Diarrhea duration, vomiting duration, return visits, missed daycare, missed work, and household transmission rate will be subject to Holm's stepdown procedure. Specifically, the smallest of the six p-values will be compared to a significance level of 0.05/6. If significance is reached, the next-smallest p-value will be compared to 0.05/5, and so on. The final p-value of the six will be compared to 0.05, assuming that all others are significant. Confirmatory and tertiary outcome results will not be adjusted for multiple comparisons, as these are more exploratory in nature.

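### Household transmission, a Holm-tested secondary outcome, has no common observation window: daily surveys end at the later of recovery and day 5, so a drug that shortens illness can show a small false reduction

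*Combined protocol and SAP*

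**What the plan says.** **Source of the data.** Protocol V3.0 sections 1.3 and 5.2 (item 6) describe a household census at enrollment, after which "information about household contacts symptoms will be obtained during daily surveys to determine household transmission rate". No other source is named.

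**When daily surveys end.** Section 3.4 says staff "will contact the family daily (including weekends) until both the diarrhea and vomiting have resolved and the treatment has been completed on day 5". Section 7.4 repeats both conditions: "Families will be contacted daily until both the diarrhea and vomiting have resolved and the treatment has been completed". Section 4.2 (Initial Study Drug Administration), describing what parents are told, is looser: "the need to communicate with the study team on a daily basis until symptoms resolve will be stressed".

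**Later contact.** Section 3.4 adds: "Additional contact will be made on day 14 for outcome assessment". Its general description of the follow-up form says staff "will inquire about ongoing symptoms, medical evaluations, treatments, child care, work absenteeism, and side effects".

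**Status in the analysis.** SAP v1.2 section 5.4 lists six secondary outcomes for multiplicity control, ending with "missed work, and household transmission rate will be subject to Holm's stepdown procedure". SAP 2.2.3 gives this outcome by name only. SAP 7.3 sets out analyses for symptom durations, missed daycare, missed work and return visits, and none for household transmission. Return visits, by contrast, have a fixed two-week window.

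**The concern.** A transmission rate can be compared between arms only if both arms are watched for the same time. Here the scheduled watching time beyond day 5 depends on how long the index child stays ill. That is a post-randomization variable, it is itself a secondary outcome, and the drug is intended to shorten it. If the drug works on duration and does nothing to spread within the household, the active arm has fewer survey days on which a sick sibling or parent can be reported, and so records fewer cases.

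The outcome carries formal weight as one of the six in the Holm family. Holm also sharpens the problem: if a real effect on duration reaches significance, the thresholds for the remaining outcomes relax, in just the situation where the window bias exists.

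Separately, an outcome that is tested but has no stated numerator, at-risk denominator, window or test leaves those choices open until the data are in hand.

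**Working it through.** The plan states no rate, power or window length for this outcome, so there is no figure of its own to reproduce. The check follows the stated contact rule with true transmission identical in both arms.

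**1. Window.** Let D be days of symptoms after randomization. Sections 3.4 and 7.4 give W = min(14, max(5, D)). Every household is due 5 days; the arms can differ only through children with D > 5.

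**2. Inputs.** From the documents: the day-5 floor, day 14, and a 25-hour shortening of diarrhea (protocol 2.1, used only for scale). Assumed, because the documents do not give them: D exponential or lognormal (log SD 0.6), placebo mean 2 to 6 days; shortening of 25 h or 20%; mean delay from randomization to household onset 2 to 5 days (early clustering), or onset spread evenly.

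**3. Worked example, exponential D.** E[W] = 5 + μ(e^(−5/μ) − e^(−14/μ)).

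- Placebo, μ = 4: 5 + 4 × (0.2865 − 0.0302) = 6.03 days; 28.7% still ill after day 5.
- Active, μ = 4 − 25/24 = 2.958: 5 + 2.958 × (0.1845 − 0.0088) = 5.52 days; 18.4% still ill.

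With evenly spread onset the false risk ratio is about 5.52/6.03 = 0.92.

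With early clustering, mean delay δ = 3 days and r = 1/δ + 1/μ, P(recorded) = 1 − e^(−5/δ) + [(1/δ)/r] × (e^(−5r) − e^(−14r)).

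- Placebo, r = 0.583: 0.811 + 0.571 × (0.0541 − 0.0003) = 0.842.
- Active, r = 0.671: 0.811 + 0.497 × (0.0348 − 0.0001) = 0.828.

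Risk ratio 0.828/0.842 = 0.984.

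**4. Across the scenarios in step 2**

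| Onset of household cases | False risk ratio |
|---|---|
| Evenly spread (ratio of mean windows) | 0.90 (5.99/6.66 days) to 0.99 (5.02/5.05 days) |
| Clustered early | 0.96 to 1.00 |
| Duration unchanged by treatment | 1.00 |

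The 0.99 end is the case where only 3% of placebo children are ill past day 5. With early clustering, about 67 to 95% of 14-day cases are recorded.

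**5. Second check, constant hazard.** Simulation, 1,000,000 children per arm: D gamma (shape 1.5), mean 96 h v 71 h; surveyed days = D in days rounded up, plus 1, limited to 5–14; the same daily chance h of a first household case in both arms; P(case) = 1 − (1 − h)^days.

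- Mean surveyed days: 6.37 v 5.71.
- h = 2%: 12.0% v 10.8%. h = 4%: 22.6% v 20.6%. Risk ratio about 0.91.
- Placebo means of 60–120 h and reductions of 12–25 h: 0.91 to 0.97.
- Full 14-day rates, 1 − (1 − h)^14: 25% and 44%.

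**6. Chance of a false claim in that less favorable case.** Take 970 × 0.90 / 2 ≈ 437 per arm and a simple two-proportion test; P(significant, favoring probiotic) = Φ(difference/SE − z).

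- 12.0 v 10.8%: SE = √[(0.1056 + 0.0963)/437] = 0.0215; 0.012/0.0215 = 0.56. At two-sided 0.05, Φ(0.56 − 1.96) ≈ 8%. At 0.05/6, Φ(0.56 − 2.64) ≈ 2%.
- 22.6 v 20.6%: SE = √[(0.1749 + 0.1636)/437] = 0.0278; 0.020/0.0278 = 0.72. At 0.05, about 11%; at 0.05/6, about 3%.

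The nominal values are 2.5% and 0.4%.

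**The case against.** **Surveys do not simply stop at recovery.** A reader might infer that a child well on day 2 leaves the household observed for 2 days. Sections 3.4 and 7.4 rule this out, since treatment must also be completed. Without the day-5 floor the early-clustering risk ratio would run from 0.54 to 0.95; with it the range is 0.96 to 1.00. The looser sentence in section 4.2 describes the instruction to parents and does not set the contact schedule. This objection stands and removes most of the bias.

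**Day-14 collection cannot be excluded.** A reader might infer from the topic list in section 3.4 that nobody asks about contacts at day 14, so that cases after day 5 are lost for most families. The list cannot bear that: it also omits household illness for the daily surveys, where section 5.2 says it is asked. The case report forms are not in the documents. What stands against the plan is that the endpoint definition names daily surveys only.

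**The size depends on assumptions.** A constant hazard is not in the documents. Children may enroll with nearly 7 days of symptoms, and the pilot data put about half at 2 days or more, so household exposure begins before randomization and early clustering is plausible. A reader might conclude from the constant-hazard figures that about half of all cases go unrecorded; that follows from the assumption, not from the plan. The 25 hours also comes from trials that the protocol itself calls flawed.

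**A false claim remains unlikely**, and a drug that leaves duration unchanged gains nothing from this bias. Both are true. They limit the size of the problem but do not supply the missing window, denominator or test.

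**Conclusion.** The concern holds in limited form. Under the stated contact rule, observation time for a Holm-tested outcome depends on illness duration beyond day 5, and nothing in the protocol or SAP sets a common window. The direction of bias favors the arm that recovers sooner.

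The size is modest: a false risk ratio of about 0.90 to 0.97 with evenly spread onset (nearer 1 when hardly any child is ill past day 5), 0.96 to 1.00 with early clustering, and exactly 1.00 with no effect on duration. These figures rest on assumed distributions of illness length and household onset, and on contacts being asked about only in daily surveys. If the day-14 form already collects contacts' illness in every family, the remedy is to write that into the definition.

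The firmest part needs no simulation: the SAP tests this outcome without stating its window, at-risk denominator or test.

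**What to change.** - Define household transmission over one window for every household: new vomiting or diarrhea, with onset from randomization to day 14, in members recorded as well in the enrollment census.
- Ask the question at the existing day-14 contact in all families, whatever the child's symptom status, and record onset dates so that later cases are not counted.
- Where day-14 data do not exist for children already enrolled, restrict the comparison to days 1 to 5, which are scheduled for every family.
- In SAP 2.2.3 and 7.3, state the numerator, the at-risk denominator (members well at census) and the test.
- Reconcile the parent-instruction sentence in protocol section 4.2 with the contact rule in 3.4 and 7.4.

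With a fixed window, fully ascertained, the risk ratio under no true effect is 1.00 by construction. The cost is one question at a contact already planned, or an analysis restriction, plus a few sentences in the SAP. The downside is some recall error at day 14, or fewer cases if only days 1 to 5 are used.

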### 5.3 Sample Size Calculations and Statistical Power

The primary analysis will be performed on a binary outcome: development of moderate-to-severe disease. The power of this analysis is based on the proportion of patients with moderate-to-severe disease. Our pilot data indicate that 25% of patients will have moderate to severe disease during the course of their illness. Furthermore expert surveys indicated that an absolute risk reduction of 10% would constitute a minimal clinically-important difference (MCID). Therefore our sample size calculation assumed a 25% event rate in the control group for which we desire to detect an absolute beneficial treatment effect of 10% with 90% power. Using a two-sided type I error ( $\alpha$ ) of 0.05 and the hypothesized proportions yields a required total sample size of 670 patients. Our expected power, should we find different event rates in our 2 groups, is displayed in [Table 2 on the next page](#).

Based on previous work by our group, we assumed a 10% loss to follow up ( $670/0.90 = 744$ ), 5% drop out, and 3% drop in (caregivers who buy a probiotic agent

Outcome Control	Outcome Intervention	% Difference	Power
0.30	0.21	9%	0.76
0.30	0.20	10%	0.85
0.25	0.15	10%	0.90
0.25	0.16	9%	0.82
0.25	0.17	8%	0.72
0.20	0.10	10%	0.95
0.20	0.12	8%	0.81
0.20	0.13	7%	0.69

Table 2: Power Analysis

to administer to their child) rate ( $744/(0.92)^2 = 879$ ). Adjustment for O’Brien-Fleming monitoring boundaries requires a further 2% increase. Thus, the total number randomized (final sample size) will be 897.

### 5.3.1 Enrichment Design

The above study design and power analysis are based on the assumption of homogeneous treatment effect. We may also incorporate an enrichment design to restore the statistical power in case the presence of a subpopulation with a substantially low treatment effect is identified. We are particularly interested in two potential subpopulations: participants with  $<2$  days of symptoms and those with  $\geq 2$  days of symptoms. Based on our pilot data, each subpopulation accounts for approximately 50% of the total population. The decision for enrollment modification will be made at the first interim analysis for efficacy. Specifically, three statistics (based on a normal approximation of binomial distribution, or z-statistics) will be calculated to compare the primary efficacy endpoint between treatment and control groups for subjects in the total population and the two subpopulations, respectively. If the z-statistic from a subpopulation is  $<0.3$  and also smaller than that in the total population, subjects from this subpopulation will no longer be considered in the subsequent enrollment. All subjects, regardless of symptom duration will be included in the final analyses. Our simulation studies have shown that such an enrichment design can increase the power considerably when the treatment effects are different across subpopulations, while it will have little impact on power when the treatment effects are similar.

### 5.3.2 Sub-group Analyses

The presence of a Modified Vesikari Score  $\geq 9$  will be analyzed by age  $<1$  year, duration of symptoms, breast-feeding status, antibiotic usage, rotavirus and norovirus positivity. A subgroup effect will be considered significant if the interaction between subgroup and treatment in a logistic regression model is significant at a Bonferroni-corrected level.

## 5.4 Recruitment Estimates and Attrition

### 5.4.1 Recruitment

To estimate the number of subjects with acute gastroenteritis of eligible ages that would meet all inclusion criteria and be enrolled annually, we obtained discharge diagnoses from all study sites for 2005-2011. In 2011, the study sites evaluated 14,048 potentially eligible subjects (patients 3-48 months with ICD9 codes for diarrhea) out of 507,039 total emergency department visits (2.8%). In the past 7 years the lowest proportion of such patients per total emergency department volume was 2.3% (2008). Therefore, using 2011 emergency department volumes and lowest proportion of patients with diarrhea our conservative estimate for eligible patients would be 11,150 patients 3-48 months with diarrhea per year (or 30 patients per day network wide). Our best estimate is that 4.5% of children with acute gastroenteritis aged 3-48 months will be enrolled. We plan to enroll 225 patients/year and 970 subjects over 4 acute gastroenteritis seasons.

### 5.4.2 Potential for Bias

Reporting bias will be minimized by adhering to CONSORT recommendations including the use of third-party assignment. Placebo capsules and active drug will be provided by I-Health Inc. The total weight of all capsules is 325 mg. The probiotic and placebo capsules and powder are identical in appearance, taste, texture, and odor. Participants, families, healthcare providers, data collectors, outcome adjudicators, and data analysts will be blinded as to intervention arm, thereby preventing bias in outcome assessment. Two DCC statisticians will be partially unblinded (with knowledge of group assignments, but not group identities) in order to present interim results to the DSMB. An intention-to-treat analysis will be performed to minimize bias associated with poor compliance and non-random loss of participants. Co-interventions (e.g. antiemetic administration, intravenous rehydration) and other potential sources of confounding will be recorded. Our use of a published validated score as an outcome measure will protect against the introduction of bias in the assessment of treatment effects.

### 5.4.3 Compliance

Noncompliance with probiotics is rarely reported in previous studies, and not expected to be problematic in this cohort. Participant withdrawal has been related mostly to the primary illness. In the Canadian pilot study, compliance was 91%. We will track compliance by obtaining information from parents during the day 5 follow-up contact. If there are any unused capsules, we will request their return (a pre-stamped, pre-addressed envelope will be provided).

### 5.4.4 Loss to Follow-up

Our previous emergency department pediatric acute gastroenteritis research studies achieved telephone follow-up rates of 98% on day 3 and 96% on day 7. Similar success has been documented in other PECARN multicenter studies (91%). We estimate a 10% loss to follow-up. If daily contact does not occur, we will collect data from missed days on subsequent days when caregivers are contacted. The use of patient diaries (paper and/or electronic) and chart review will supplement parent contact. Based on our pilot trial we have devised the following strategies to maximize follow-up: all follow-up procedures will be centralized at the lead institution and conducted by experienced study staff; we will obtain multiple phone numbers from caregivers as well as emergency contacts, and we will schedule calls and send reminders prior to the call if preferred. Finally, electronic diary filing and transmission may be available for interested families.

### 5.4.5 Compensation

Financial compensation may be provided to compensate for parent's time completing follow-up. This compensation must be approved by each site's Institutional Review Board.

## 6 Data Management

### 6.1 Clinical Sites

Study data will be recorded on paper work forms or by direct data entry into an electronic data capture (EDC) system. If paper work forms are used they will be retained at the clinical site. The data from the work forms will then be entered into the EDC system provided by the Data Coordinating Center at the University of Utah School of Medicine.

The clinical investigator at each participating site will complete a Form FDA 1572, Statement of Investigator. That individual is responsible for all aspects of study imple-

mentation, including administration of study drug, collection of accurate study data, and correct entry of the data into the EDC. These tasks may be specifically delegated to other individuals at the clinical site, but the clinical investigator is responsible to supervise all aspects of the study, and is responsible to assure that all staff involved in this study are adequately trained to perform the delegated tasks. All local research records will remain in a locked file in a secure room unless being used by research staff, and all computerized information will be maintained on password protected computers.

